6.6.2. Restricted Medications and Procedures

The following are permitted during the study under specified conditions:

- Short-term use of systemic corticosteroids may be permitted to treat acute AEs (eg, asthma, croup) during the LTS period, and the decision to keep the participant in the study (or to permanently discontinue study cream) will be made in consultation with the medical monitor.
- Participants may continue using sedating antihistaminic drugs as long as their use is part of a preexisting and well-established regimen. There are no restrictions for use of nonsedating antihistamines.

- Use of any over-the-counter, nonprescription preparations deemed acceptable by the investigator is permitted under an established and stable treatment regimen.
- Use of any prescription medication (including phytotherapeutic, herbal, or plant-derived preparations) within 7 days before the baseline visit through the safety follow-up visit, unless deemed acceptable by the investigator.
- Immunizations with a live-attenuated vaccine are not recommended during the VC period (first 8 weeks) unless deemed necessary by the investigator.
- Allergen immunotherapy (desensitization) that is ongoing at a stable dose at the time of study entry may be continued while on study but only at the same dose.
- Bleach baths are allowed as long as they do not exceed 2 baths per week and their frequency remains the same throughout the study.
- Participants should not take baths or showers within 2 hours after study cream application.
- Topical anti-infectives or other topical treatments applied to active AD lesions should not be used for at least 4 hours before and 2 hours after application of study cream.

6.6.3. Prohibited Medications and Procedures

The following are not permitted during the study:

- Any investigational medication other than the study cream.
- Topical corticosteroids, tacrolimus, pimecrolimus, and PDE4-inhibitors (Eucrisa).
- Other topical agents for AD (except bland emollients as noted in Section 6.6.1).
- Treatment known to affect the course of AD.
- Systemic corticosteroids (except the example stated in Section 6.6.2), methotrexate, cyclosporin A, azathioprine and biologic therapies, or other immunosuppressant agents.
- Phototherapy or tanning beds.

6.7. Treatment After the End of the Study

There will be no treatment provided after the end of the study.

7. DISCONTINUATION OF STUDY TREATMENT AND PARTICIPANT WITHDRAWAL

7.1. Discontinuation of Study Treatment

7.1.1. Reasons for Discontinuation

Participants **must** be discontinued from study treatment for the following reasons:

- Lack of efficacy response during the LTS period (defined as no change/improvement in either %BSA or IGA when treated continuously for 8 weeks).
- AD worsens during either the VC period or the LTS period, to the point where the extent of AD to be treated (ie. all areas excluding the scalp) exceeds 20% BSA.
- The participant becomes pregnant.
- Consent is withdrawn.
Note: Consent withdrawn means that the participant has explicitly indicated that he/she does not want to be followed any longer; in this case, no further data, except data in the public domain, may be solicited from or collected on the participant.
Participants may choose to discontinue study treatment and remain in the study to be followed for safety monitoring.
- Further participation would be injurious to the participant's health or well-being, in the investigator's medical judgment.
- Any AE of unacceptable severity as noted in Section [6.5.2](#).
- The study is terminated by the sponsor.
- The study is terminated by the local health authority, IRB, or IEC.

A participant **may** be discontinued from study treatment as follows:

- If, after 2 consecutive study visits and reinforcement of study cream application by site staff, a participant's drug usage exceeds one 60-g tube every 4 days, a participant who again fails to meet compliance benchmarks at a subsequent visit may be considered for withdrawal from the study. The medical monitor should be consulted for instruction on handling the participant.
- If, during the course of the study, a participant is found not to have met eligibility criteria, the medical monitor, in collaboration with the investigator, will determine whether the participant should be withdrawn from study treatment.
- If a participant is noncompliant with study procedures or study cream administration in the investigator's opinion, the medical monitor should be consulted for instruction on handling the participant.

7.1.2. Discontinuation Procedures

In the event that the decision is made to permanently discontinue the study treatment prior to the Week 52/EOT study visit, the ET visit should be conducted. Reasonable efforts should be made to have the participant return for a follow-up visit. The date of the last application of study cream and the reason for discontinuation of study cream will be recorded in the eCRF.

If a participant is discontinued from study treatment:

- The study monitor or sponsor must be notified.
- The reason(s) for withdrawal must be documented in the participant's medical record and the primary reason for withdrawal must be included in the eCRF.
- The ET visit should be performed.
- The date of the ET visit should be recorded in the eCRF.
- Participants must be followed for safety until the time of the follow-up visit or until study treatment-related AEs resolve, return to baseline, or are deemed irreversible, whichever is longest.

If the participant discontinues study treatment and actively withdraws consent for collection of follow-up data (safety follow-up), then no additional data collection should occur; however, participants will have the option of withdrawing consent for study treatment but continuing in the follow-up period of the study for safety assessments.

7.2. Participant Withdrawal From the Study

A participant may withdraw from the study at any time at his/her own request or may be withdrawn at any time at the discretion of the investigator for safety, behavioral, compliance, or administrative reasons.

If the participant withdraws consent for disclosure of future information, the sponsor may retain and continue to use any data collected before such a withdrawal of consent. If a participant withdraws from the study, he/she may request destruction of any samples taken and not tested, and the investigator must document this in the site study records.

Data to be collected at the time of study discontinuation and follow-up and for any further evaluations should conform to the requirements of the ET/EOT visit (see [Table 3](#) and [Table 4](#)).

7.3. Lost to Follow-Up

A participant will be considered lost to follow-up if he/she repeatedly fails to return for scheduled visits and is unable to be contacted by the study site. The following actions must be taken if a participant fails to return to the clinic for a required study visit:

- The site must attempt to contact the participant and reschedule the missed visit as soon as possible and counsel the participant on the importance of maintaining the assigned visit schedule and ascertain whether or not the participant wishes to and/or should continue in the study.

- Before a participant is deemed lost to follow-up, the investigator or designee must make a reasonable effort to regain contact with the participant (where possible, 3 telephone calls and, if unsuccessful, a certified letter to the participant's last known mailing address or local equivalent methods). These contact attempts should be documented in the participant's medical record.
- Should the participant continue to be unreachable, he/she will be considered to have withdrawn from the study.

8. STUDY ASSESSMENTS AND PROCEDURES

See [Appendix C](#) for COVID-19-related guidance.

8.1. Administrative and General Procedures

8.1.1. Informed Consent Process

- The investigator or his/her representative will explain the nature of the study to the participant or his/her legally authorized representative and answer all questions regarding the study.
 - Informed consent/assent must be obtained before any study-related procedures are conducted, unless otherwise specified by the Protocol.
 - Informed consent/assent must be obtained using the IRB/IEC-approved version in a language that is native and understandable to the participant. A template will be provided by the sponsor or its designee. The sponsor or its designee must review and acknowledge the site-specific changes to the ICF/assent template. The ICF must include a statement that the sponsor or its designee and regulatory authorities have direct access to participant records.
 - The ICF must contain all required elements and describe the nature, scope, and possible consequences of the study in a form understandable to the study participant.
- Participants must be informed that their participation is voluntary. Participants or their legally authorized representative will be required to sign a statement of informed consent/assent that meets the applicable requirements and regulations for the countries in which the study is being conducted as well as the IRB/IEC or study center.
- The participant must be informed that his/her personal study-related data will be used by the sponsor in accordance with local data protection laws. The level of disclosure must also be explained to the participant.
- The participant must be informed that his/her medical records may be examined by Clinical Quality Assurance auditors or other authorized personnel appointed by the sponsor, by appropriate IRB/IEC members, and by inspectors from regulatory authorities.

- The medical record must include a statement that written informed consent/assent was obtained before the participant was enrolled in the study and the date the written consent was obtained. The authorized person obtaining the informed consent must also sign the ICF/assent.
- Participants must provide consent to the most current version of the ICF(s)/assent(s) during their participation in the study.
- A copy of the signed ICF(s)/assent(s) must be provided to the participant or the participant's legally authorized representative.
- Participants who are rescreened are required to sign a new ICF/assent (if rescreened > 28 days after the initial screening [or > 35 days for participants on prior medications requiring a 4-week washout period as described in Section 5.2, Exclusion Criterion 6b]) and must be assigned a new participant number.

8.1.2. Screening Procedures

Screening is the interval between signing the ICF/assent and the day the participant is enrolled in the study (Day 1). Informed consent (or assent) must be obtained before performing any study-specific procedures. Screening assessments for determination of eligibility may be performed over a period of up to 28 days, or up to 35 days for participants on prior medications requiring a 4-week washout period as described in Section 5.2 (Exclusion Criterion 6b).

Assessments that are required to demonstrate eligibility may be performed over the course of 1 or more days during the screening process.

Results from the screening visit evaluations will be reviewed to confirm eligibility before enrollment or the administration of study cream. Tests with results that fail eligibility requirements may be repeated once during screening if the investigator believes the results to be in error. For screening assessments that are repeated, the most recent available laboratory results before randomization/treatment assignment will be used to determine eligibility. Additionally, a participant who fails screening may repeat the screening process 1 time if the investigator believes that there has been a change in eligibility status (eg, after recovery from an infection). The participant is not required to sign another ICF if the rescreening occurs within 28 days (or 35 days for participants on prior medications requiring a 4-week washout period) of the previous ICF signature date (screening period).

See Section 5.4 for information regarding screen failures and the rescreening procedure for participants.

8.1.3. Interactive Response Technology Procedure

Each participant will be identified in the study by a participant ID number, which is a combination of the site ID and participant number. Site staff should contact the IRT system to obtain the participant ID number during screening. Upon determining that the participant is eligible for study entry, the IRT system will be contacted to obtain the study medication kit assignment. Additionally, the IRT system will be contacted at each regular study visit during both the VC period and the LTS period as indicated in Table 3 and Table 4 to update the study cream supply. The IRT system will also be used during the study visits to recalculate the amount of study cream to be dispensed if the participant's %BSA of AD lesions to be treated has

increased (during the VC period) or has either increased or decreased (during the LTS period). Additional details are provided in the IRT Manual.

8.1.4. Distribution of Reminder Cards and Diaries

Starting at Day 1 visit and each visit thereafter, a study cream-specific diary will be given to each participant in order to record use of the study cream. The completed diary will be reviewed during each of the participant's study visits and data uploaded will be confirmed by the study staff.

Qualified clinical study staff will review the participants' entries for compliance. Participants who are noncompliant with their study cream schedule (defined as < 80% or > 120% of the expected number of applications between study visits) will have their administration instructions reinforced by the investigator or a qualified designee. Participants will be considered compliant with the treatment regimen if they apply at least 80% but no more than 120% of the expected applications during participation in the VC period of the study.

Participants will be provided with a reminder card starting on Day 1 and at all VC and all LTS visits through Week 48. The reminder card will indicate the date and time of the next visit and will also remind the participant that their morning application of study cream will be take place at the clinic under site supervision [REDACTED] safety evaluations have been completed.

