6.1.1. Study Treatment Application Guidance

Participants should remove Study Cream from the tube and apply the Study Cream with their fingertip in small amounts until all of the areas to be treated are covered by a thin, even film (see Figure 8).

Figure 8: Study Cream Application Using a Fingertip

Source: DermNet New Zealand (www.dermnetnz.org).

In the clinic, the amount of study cream used will be determined by weighing a tube(s) before and after the participant or guardian applies a thin film of study cream to the affected areas.

On the day of a visit, the participant should not apply their morning application of study cream at home; instead, study cream will be applied in the clinic during the visit, under direct supervision of the site staff. The tube will be weighed before and after application to determine the participant's usage.

Application instructions will be provided by the site study staff, and the participants will record their daily applications via a diary card provided at each study visit. Participants must not apply study cream more often than BID. Refer to the Study Reference Manual for participant instructions for handling study cream.

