6.4. Study Treatment Compliance

Compliance will be assessed for frequency of administration of study cream by reviewing the participants' diaries. Participants will also be questioned regarding study cream application technique, missed applications, and use of any additional topical or systemic prescriptions of other products or over-the-counter products. Compliance with study cream will be evaluated by the participant's adherence to the BID application regimen (evaluation of actual number vs prescribed number of applications) and documented by the site staff and monitored by the sponsor/designee.

Qualified clinical staff will review the diary entries for compliance. Participants will be considered compliant with the treatment regimen if they apply at least 80% but no more than 120% of the prescribed number of applications during participation in the VC period of the study. Participants who are noncompliant during the VC period and LTS period (if on a treatment cycle) will be reinstructed by the investigator (or designee), and the sponsor should be consulted by the investigator for instruction on the proper handling of the participant.

Drug accountability will be assessed by documenting the quantities of drug used between study visits (tube counts and weighing). At the first clinic visit and subsequent study visits, the amount of study cream to be applied is to be determined by weighing a tube before and after the participant applies a thin film of study cream to the affected areas. Participants will be instructed to bring all study cream with them to the study visits in order for site personnel to assess study cream accountability.

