10.2. Populations for Analysis

[Table 12](#) presents the populations for analysis.

Table 12: Populations for Analysis

Population	Description
ITT	The ITT population includes all randomized participants. Treatment groups for this population will be defined according to the treatment assignment at randomization.
PP	The PP population includes randomized participants who are considered to be sufficiently compliant with the Protocol. In general, the following are important protocol deviations that may significantly affect the primary analysis: Missing data for the primary endpoint Overall application compliance less than 80% during the VC period Participants with one or more such deviations will be excluded from the PP population. In addition, important protocol deviations related to inclusion/exclusion criteria, discontinuation criteria, and use of prohibited concomitant medications will be reviewed. Decisions as to whether any of these deviations warrant exclusion from the PP population will be made prior to unblinding.
Safety	The safety evaluable population includes all participants who applied study cream at least once. Treatment groups for this population will be determined according to the actual treatment the participant received on Day 1.
LTS evaluable	All analyses for the LTS period will be conducted with the LTS evaluable population, which includes all participants who applied study cream at least once during the LTS period.
	[REDACTED]

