5.3.2. Per Protocol Population

Participants in the ITT population who are considered to be sufficiently compliant with the Protocol compose the PP population, which is defined for supportive sensitivity analyses for the primary endpoint in the VC period. Participants with important protocol deviations, as defined in Section 6.3, will be excluded from the PP population.

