6.3. Protocol Deviations

In general, the following are important protocol deviations that may significantly affect the primary analysis:

- Missing data for the primary endpoint
- Overall application compliance < 80% during the VC period
- Did not apply any study cream in the VC period
- IGA assessment 14 days out of the target visit date at Week 8 (Day 57 ±7)

Participants with any of the deviations listed above will be excluded from the PP population. Additionally, important protocol deviations, such as those related to inclusion/exclusion criteria, discontinuation criteria, and the use of prohibited concomitant medications, will be reviewed. Decisions as to whether any of these deviations warrant exclusion from the PP population will be made prior to unblinding.

Protocol deviations will be summarized and listed by treatment groups in the VC and LTS periods separately.

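### The automatic per-protocol exclusion uses only the lower of the protocol's two compliance limits, so a child above 120% of applications stays in the PP set unless a discretionary review removes them

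*Protocol*

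**What the plan says.** **Compliance definition.** Protocol 8.1.4 treats as compliant those who, over the vehicle-controlled (VC) period, meet both limits: "if they apply at least 80% but no more than 120% of the expected applications during participation in the VC period". Protocol 6.4 repeats the band: "at least 80% but no more than 120% of the prescribed number of applications during participation in the VC period". For re-instruction at visits, 8.1.4 also labels noncompliance in both directions, "defined as < 80% or > 120% of the expected number of applications between study visits". Protocol 6.1.1 sets the frequency ceiling: "Participants must not apply study cream more often than BID".

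**PP definition.** SAP 5.3.2 states the intent: "Participants in the ITT population who are considered to be sufficiently compliant with the Protocol compose the PP population". The compliance item that implements it has one side only. Protocol Table 12 has "Overall application compliance less than 80% during the VC period" and SAP 6.3 has "Overall application compliance < 80% during the VC period". The consequence is automatic: "Participants with any of the deviations listed above will be excluded from the PP population".

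**Other exclusions.** The remaining automatic items are missing primary endpoint data and, in the SAP only, no cream applied and a Week 8 IGA outside its window. None concerns over-application. Both documents add a case-by-case review of other important deviations, decided before unblinding, and name eligibility, discontinuation criteria and prohibited medication.

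**The concern.** The PP analysis refits the primary model in children who followed the protocol closely enough, as support for the ITT result. The plan takes its PP cutoff of 80% from the same band that 6.4 and 8.1.4 use, but leaves out the other end of that band without giving a reason. A child at 79% is removed by rule. A child at 121%, whom the protocol equally places outside the compliant range, is kept unless someone decides otherwise. What is at stake is whether the PP set can be described as compliant in the protocol's own sense, and whether its membership rests on a fixed rule or on judgement.

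**Working it through.** **1. Can the computed compliance exceed 120%?** SAP 6.5 defines it as

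100 × (applications actually made) / (planned applications − interrupted applications).

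The numerator is not capped and the section sets no upper limit. Values above 120% can occur, and the rule as written would pass them.

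**2. Where the limits fall.** Inputs: an 8-week VC period with twice-daily application (Protocol 4.1).

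- Planned applications: 8 × 7 × 2 = 112.
- Lower limit: 0.80 × 112 = 89.6.
- Upper limit: 1.20 × 112 = 134.4, so 135 or more exceeds it. That is 135/56 = 2.41 per day on average.
- With 14 interrupted applications: 1.20 × 98 = 117.6, so 118 or more.
- With 28 interrupted applications: 1.20 × 84 = 100.8, so 101 or more.

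The visit window makes 112 approximate for an individual child.

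**3. What removing one child does to a PP rate.** Inputs: planned arms of 126, 126 and 63 (Protocol Table 2); assumed IGA-TS rates of 51%, 47% and 14% (Protocol 10.1). With n children and rate p, removing a responder lowers the rate by (1 − p)/(n − 1). Removing a nonresponder raises it by p/(n − 1).

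| Arm | Responder removed | Nonresponder removed |
|---|---|---|
| 1.5%, n = 126 | 0.49/125 = 0.39 points | 0.51/125 = 0.41 points |
| 0.75%, n = 126 | 0.53/125 = 0.42 points | 0.47/125 = 0.38 points |
| Vehicle, n = 63 | 0.86/62 = 1.39 points | 0.14/62 = 0.23 points |

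The largest shifts are about 0.4 points (active) and 1.4 points (vehicle), in either direction.

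**4. Does the stricter rule cost precision that matters?** The plan's own figure first: Protocol 10.1 states more than 95% power by Fisher's exact test at two-sided alpha 0.025. Exact enumeration with 126 versus 63 gives 99.9% (51% vs 14%) and 99.5% (47% vs 14%), which agrees.

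The documents give no rate of over-application, so the losses below are assumptions, applied equally to each arm.

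| Assumed loss | Arm sizes (active, vehicle) | 1.5% vs vehicle | 0.75% vs vehicle |
|---|---|---|---|
| 5% | 120, 60 | 99.9% | 99.2% |
| 10% | 113, 57 | 99.7% | 98.7% |
| 20% | 101, 50 | 99.4% | 97.6% |

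Even an implausibly large loss leaves the comparison above the stated 95%.

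**The case against.** **A route to exclusion already exists.** SAP 6.3 introduces its review list as examples, so the list is open, and discontinuation criteria are among those named. Protocol 7.1.1 allows discontinuation for heavy tube use with repeated failure on compliance, or for noncompliance with cream administration. A reader might infer from the one-sided item that nothing in the plan can remove an over-applier. The documents do not support that. What stands is narrower: removal on the high side is discretionary, and on the low side it is automatic.

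**The band and the PP rule serve different purposes.** The band in 6.4 and 8.1.4 drives re-instruction and consultation with the sponsor. The PP set asks only for sufficient compliance, and neither document says it must equal the compliant set. The Amendment 6 summary records that the PP cutoff moved from 60% to 80% with the reason redacted, so an oversight cannot be inferred. This is fair. The asymmetry may be deliberate, but the plan does not say so.

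**The 120% limit still tolerates use beyond twice daily.** True, but the point is consistency with the protocol's own tolerance, which is 20% on each side.

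**Few children, if any, will qualify.** Averaging more than 2.4 applications a day, despite the ceiling and re-instruction at visits, is probably uncommon. This stands and limits the importance of the point.

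**Conclusion.** The point holds as a minor inconsistency. The protocol's compliance definition has two limits and the automatic PP exclusion has one, so a child above 120% stays in the PP set by default.

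Two stronger readings should be resisted. A reader might infer that keeping these children credits extra dosing to the active arms and inflates the PP effect. Nothing in the documents shows which arm over-applies or how such children respond. They could be on vehicle, or could be poor responders, so the direction is unknown. A reader might also size the effect as 1/126 = 0.8 points or 1/63 = 1.6 points per child. That is the effect of reversing one child's outcome. Exclusion takes the child out of numerator and denominator, which gives at most about 0.4 and 1.4 points.

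Those sizes rest on the planned arm sizes and assumed response rates, and would be somewhat larger per child in a smaller PP set. The number affected is unknown and probably small. The PP analysis is supportive and outside the alpha-controlled tests. The ITT primary analysis, its alpha and the sample size are unaffected.

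**What to change.** Before unblinding, extend the compliance item in Protocol Table 12 and SAP 6.3 so that overall application compliance below 80% or above 120% over the VC period is an excluding deviation, matching 6.4 and 8.1.4. If the sponsor means to keep over-appliers, a sentence saying so and giving the reason would also settle the inconsistency, though it would leave the PP set outside the protocol's own compliance band.

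The cost is one phrase in two places and one programming condition. The downside is possibly a few fewer children in a supportive analysis. Only the analysis population changes; no treatment rule is touched.

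One companion clarification is worthwhile. Protocol 6.5.1 lets cream be withheld at one site and continued elsewhere, recorded as an interruption. SAP 6.5 should say whether such partial interruptions reduce the denominator. If they do, a child who made all 112 applications with 19 recorded as interrupted would show 112/93 = 120.4% and be flagged without having over-applied.
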